Acknowledging the benefits of combined electrotherapy and KOA as a progressive and degenerative condition with unlikely regression or restoration of damaged structures, the study aims to investigate the effects of stimulation assisted activities to delay the disease progression and muscle atrophy in those with KOA. Thus, the purpose of this research is to investigate if stimulation assisted (NMES and FES) activities can combat disuse atrophy for individuals diagnosed with KOA. This study will use a home-based medical device (Cionic Neural Sleeve NS-100, K213622, CIONIC, San Francisco, CA) to administer electrical stimulation and measure its effect on outcomes that include quadriceps strength, perceived functional capacity, pain, and walking performance.

Significance

Adults with KOA spend most of their day engaging in sedentary behavior and report worse physical function⁸, which may lead to progression of the condition, increased functional dependence and decreased quality of life²². Existing literature shows that NMES assisted exercise may counter disuse atrophy in sedentary individuals²³, but because there has been minimal research investigating the effects of FES in the KOA community, exploration of this study is warranted.

Figure 1: Cionic Neural Sleeve system

Note: Left: Cionic Neural Sleeve showing the configuration of the FES and electromyographic (EMG) electrode arrays. Center: Cionic mobile application interface for setting FES parameters (frequency, pulse width, intensity) and current field steering. Right: Cionic Neural Sleeve on body.

Research Objectives

1. Analyze the effects of electrical stimulation assisted interventions versus a conventional exercise program on muscle strength, perceived function, and pain in KOA.
2. Compare the effects of unassisted walking and stimulation assisted walking on walking performance in KOA.
3. Measure the compliance of electrical stimulation assisted interventions to a conventional exercise program on the effects of pain and perceived function in KOA.

Hypotheses

It was hypothesized that combined electrotherapy groups will show larger muscle mass and strength improvements; improved gait kinematics, pain and perceived function; and a high compliance to the assigned program compared to the unstimulated group.

Specific Aims

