A sample size of 32 participants was calculated to be sufficient for a two-tailed significance level of 5% and a power of 80% (Appendix A). This was adjusted to 45 participants with knee osteoarthritis to allow for dropouts. Recruitment for this study will be conducted using a recruitment flyer and through the CIONIC website. Recruitment will be based on a first come

basis. Interested participants will complete a questionnaire to be reviewed according to the inclusion and exclusion criteria. Responses will then be reviewed, and prospective participants will be invited to schedule a virtual meeting with a study staff member who will screen the prospective subject for an understanding of the study and for their voluntary participation. All participants will be assigned a unique number using a computer random number generator and randomly assigned to a group by a researcher. All participants will receive their assigned intervention at their first lab visit.

Inclusion Criteria

- Persons with knee osteoarthritis between the ages of 22 and 75
- Ability to walk a duration of 30 minutes per walking session (with or without an assistive device), for three days per week
- Able to tolerate the device for up to 1 hour per lab session
- No recent change in medication or exacerbation of symptoms over the last 60 days
- Radiographic KOA K&L grade 2 or 3 or physician diagnosed mild or moderate KOA if radiographic imaging is not available
- No hyaluronic acid or cortisone injection into knees in previous 12 months

Exclusion Criteria

- Lower motor neuron disease or injury (e.g. peripheral neuropathy) that may impair response to stimulation
- Absent sensation in the impacted or more impacted leg

- Inadequate response to stimulation, as defined as inability to achieve muscle contraction or tolerate stimulation
- Inability to ambulate with the sleeve in place of an ankle foot orthosis (AFO)/knee ankle foot orthosis (KAFO) if utilized
- Use of FES devices in the past year
- Demand-type cardiac pacemaker or defibrillator
- Malignant tumor in the impacted or more impacted leg
- Existing thrombosis in the impacted or more impacted leg
- Fracture or dislocation in the impacted or more impacted leg that could be adversely affected by motion from stimulation
- History of knee surgery
- History of other types of arthritis
- History of neurological disease
- History of seizures or diagnosed with epilepsy/seizures
- Current pregnancy

Methodology

Overview of Study

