This study is a randomized controlled trial. Figure 2 depicts a flow diagram of the study design. Participants will be screened for eligibility through a questionnaire, and after study details are explained and consent is obtained, they will be invited to the study site. Assessments will be conducted at CIONIC Inc., and involve approximately 45 patients for a 12 week study period.

CIONIC

CIONC FOR ORTHOPEDICS

All subjects will be assigned an electrical stimulation system to wear on the most impacted leg and be prescribed a home-based exercise and walking program. Subjects will be randomly assigned into three groups: (a) control; (b) NMES+; (c) NMES+FES. The control group will not receive stimulation for the exercise and walking program, whereas subjects in NMES+ will receive stimulation during exercises, and subjects in the NMES+FES group will receive stimulation during exercises and walking. Outcome measures will be assessed at baseline, 6 weeks after baseline, and end of study (Table 2). Equipment and additional feedback will be collected at the end of study. These three groups will be analyzed using several outcome measures. Primary outcome measures of the study are quadriceps strength, perceived functional capacity, self-reported pain, and walking performance. Secondary interest will be adherence to program, thigh muscle volume, functional ability of the lower limb, and quality of life. The CIONIC system will be used to track adherence (duration of sessions, frequency of use).

[figure not shown]

Figure 2: Study flow

Table 2: Study overview

Comparison Groups	Treatment Schedule	Timing and Outcome Measures
Control (unstimulated exercise and walking)	Exercise: 5x/week for 12 weeks Progression every 3 weeks	At baseline, midpoint and end of study: Quadriceps strength Perceived functional capacity Self-reported pain Walking performance Thigh muscle volume Functional ability of lower limb Quality of life EMG activity
NMES+ (NMES+exercise and unstimulated walking)	Walking: 10 min, 3x/week for 12 weeks Progression up to 30 min by end of study	Weekly: Adherence to program
NMES+FES (NMES+exercise and FES+walking)		

Participant Identification, Recruitment & Informed Consent

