Other information to be collected include date of birth, gender, ethnicity, height, weight, duration of condition, and type and dosage of medication.

Data Analysis/Statistical Analysis

For each of the primary and secondary measures, we will perform a Shapiro-Wilk test for normality to assess the assumption of normality. If the outcome variable is approximately normally distributed, a paired t-test will be used to statistically compare outcome metrics before and after the intervention within a condition. If the normality assumption is not met, the Wilcoxon signed rank test will be used as an alternative to the paired t-test for this statistical comparison. Bonferroni multiple hypothesis correction will be utilized for a corrected significance level.

To compare across conditions, an analysis of variance (ANOVA) test will be performed if the outcome variable is normally distributed. If the normality assumption is not met, the Kruskal Wallis test will be used as the non-parametric version of ANOVA. We may also employ a repeated measures ANOVA test for inclusion of all three timepoints.

Organizational Relationships

CIONIC works closely with Edge Analytics, a consulting firm who has been contracting for CIONIC for over two years. The firm is primarily responsible for algorithm development and statistical analyses of kinematic and EMG data. [name], [name], and [name] are employees of Edge Analytics who have been working closely with Cionic. [name] is a sub-investigator on this study.

Risk & Benefit Assessment

The Cionic Neural Sleeve has been tested extensively in previous studies. Across these prior studies, the Cionic Neural Sleeve has been evaluated for walking and exercise mode, approved for FDA 510k submission and its intended use in a simulated home environment, and for home usability with no adverse events.

However, any study of this kind comes with some known risks, that although rare, are associated with participation:

- Discomfort from the electrical stimulation
- Minor skin irritation at the sites of sensor/electrode pad placement
- Muscle fatigue from prolonged device use
- Anxiousness due to the anticipation of receiving an electrical stimulation
- Injury caused by unintended falls while using the Cionic Neural Sleeve
- Exposure to coronavirus disease 2019 (COVID-19) or other communicable disease

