Appendix A: Power Analysis

Power and Significance Level

[figure not shown]
These are set to standard,

Power = 0.8

Significance Level (alpha) = 0.05

Metric	Effect Size used in calculation	Required sample size when comparing participants' sessions (paired sample)	Required sample size when comparing group A to group B
WOMAC - Function bivariate	0.71 ²⁷	18	32
WOMAC - Pain bivariate	0.41 ²⁷	49	94
WOMAC - Function Standing/Walking bivariate	0.45 ²⁷	41	78

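### The 32 in Appendix A is a per-group number used as the whole-trial total, so the between-group WOMAC-Function comparison has about 47% power at 15 v 15, not 80%

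*Combined protocol and SAP*

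**What the plan says.** Participation Selection and Randomization gives the sample size: "A sample size of 32 participants was calculated to be sufficient for a two-tailed significance level of 5% and a power of 80" per cent, citing Appendix A. It continues: "This was adjusted to 45 participants with knee osteoarthritis to allow for dropouts". No dropout rate is given.

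Appendix A sets power at 0.8 and alpha at 0.05. It lists three WOMAC measures, each with an effect size, a paired-sample requirement and a requirement under the heading "Required sample size when comparing group A to group B". The number 32 appears there once, for WOMAC-Function at effect size 0.71. The heading does not say whether the entry is per group or a total.

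Overview of Study says that assessments will "involve approximately 45 patients for a 12 week study period", and then: "Subjects will be randomly assigned into three groups: (a) control; (b) NMES+; (c) NMES+FES". The readable text gives no allocation ratio. The first research objective is to "Analyze the effects of electrical stimulation assisted interventions versus a conventional exercise program on muscle strength, perceived function, and pain in KOA". Perceived function and pain are both listed as primary outcomes. The analysis section says: "To compare across conditions, an analysis of variance (ANOVA) test will be performed if the outcome variable is normally distributed". Kruskal-Wallis is the fallback, and a repeated measures ANOVA is mentioned as optional.

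**The concern.** A standardised difference of 0.71 is moderate to large, but 32 people in total is still too few to detect it between two groups with 80% power, and here the total is shared among three. The obvious explanation is that a per-group output was carried into the protocol as a total.

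This is the only sample-size justification in the protocol, and it supports the between-group comparison in the first objective. If it is wrong, readers will take the trial as having a four-in-five chance of detecting the assumed effect on function when the chance is nearer one in two or one in three. A non-significant result could then be read as evidence of no benefit.

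**Working it through.** **Inputs.** Alpha 0.05 two-sided and power 0.80 (Participation Selection and Randomization; Appendix A). Effect sizes 0.71, 0.41 and 0.45 (Appendix A). About 45 participants in three groups (Overview of Study). Assumptions: equal allocation where 15 or 11 per group is used; 0.71 read as the between-group difference in units of the analysed SD; no multiplicity correction.

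**Step 1: reproduce Appendix A.** The normal approximation per group is n = 2(1.960 + 0.842)²/d². At d = 0.71 this is 2 × 7.849/0.504 = 31.1, rounded up to 32. The exact requirement solves the noncentral-t power equation for 80%.

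| Measure | d | Two-sample n per group, exact t | Appendix A, two-group | Paired n, exact t | Appendix A, paired |
|---|---|---|---|---|---|
| WOMAC-Function | 0.71 | 32.13 | 32 | 17.59 | 18 |
| WOMAC-Pain | 0.41 | 94.35 | 94 | 48.65 | 49 |
| WOMAC-Function Standing/Walking | 0.45 | 78.49 | 78 | 40.72 | 41 |

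All six entries reproduce if the two-group column is per group. As a two-group total at d = 0.71, the requirement would be 64 to 66 two-sided, or 50 to 52 even one-sided. Three-group ANOVA totals tried were 23 (f = 0.71), 80 (f = 0.355), 90 (one group differs by 0.71) and 118 (range 0.71, third group midway). None is 32.

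**Step 2: power at the planned size, WOMAC-Function.** For an unadjusted two-sample t-test, the noncentrality is 0.71 × √(n₁n₂/(n₁+n₂)) on n₁+n₂−2 degrees of freedom. At 15 v 15 this is 0.71 × √7.5 = 1.944 on 28 df, with critical value 2.048, giving power 0.467. The other cases follow in the same way.

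| Comparison | Power |
|---|---|
| 11 v 11 (about 32 completers over three groups) | 35% |
| 15 v 15 (45 over three groups) | 47% |
| 16 v 16 (all 32 in two groups) | 49% |
| 30 v 15 (both stimulation groups pooled v control) | 59% |
| 22 v 23 (all 45 in two groups, third empty) | 64% |
| 32 v 32 | 79.8% |

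A search over every pair of group sizes summing to at most 45 puts the maximum at 22 v 23. The normal approximation gives 49% at 15 v 15 and 66% at 22 v 23, which changes nothing.

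**Step 3: the planned omnibus test.** For one-way ANOVA with three groups and a largest difference of 0.71 SD, f = 0.71/√6 = 0.290 (third group midway) or 0.71√2/3 = 0.335 (one group differs). Power is 37% or 48% at N = 45, and 27% or 34% at N = 32.

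**Step 4: related figures.** The analysis section plans paired tests within a condition. Read that way, 18 per group needs 3 × 18 = 54 people, more than 45. Paired power at d = 0.71 is 72% with 15 and 57% with 11. For WOMAC-Pain (d = 0.41), 15 v 15 gives 19%. The smallest between-group effect with 80% power is d = 1.06 at 15 per group and 1.26 at 11 per group.

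**The case against.** **The 64% ceiling is specific to one test.** This is right. It holds for an unadjusted two-sample t-test. A baseline-adjusted analysis divides the effect size by √(1−r²). With an assumed baseline correlation r of 0.5 to 0.7, power at 15 v 15 becomes 58% to 75%, still short of 80%. At r = 0.7, however, pooled stimulation v control (30 v 15) would reach 87%, and 22 v 23 would reach 90%. The plan specifies neither baseline adjustment nor a pooled contrast and gives no correlation, so this cannot support the stated 80%. The optional repeated measures ANOVA cannot be evaluated for the same reason, and Appendix A's numbers do not come from it.

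**The meaning of 0.71 cannot be checked.** It comes from a cited study and is used for both the paired and the two-group columns. Whether it is scaled to the baseline SD or the SD of change is not stated. The powers above are therefore conditional on it. The mismatch between 32 per group and 32 in total is not, because it follows from the plan's own table.

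**The paired column may refer to all participants.** Its heading does not say within each group, and 45 exceeds 18. The per-group reading rests on the analysis section. This is a side point.

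**Figures are missing from the copy reviewed,** including one in Appendix A and the study flow. They might label the column or show the allocation. A per-group label would confirm the reading here, and the ceiling does not depend on allocation.

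**Only wording changes, so the matter may seem minor.** The trial would indeed remain as underpowered as before. But the statement to be corrected is the protocol's sole claim about power, and it is wrong as written.

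**Conclusion.** The concern holds. Appendix A's 32 is a per-group requirement that the protocol uses as the total for a three-group trial. For WOMAC-Function, the outcome the 32 comes from, between-group power is roughly half the stated 80% or a little more: about 47% at 15 v 15 and 35% at 11 v 11. No split of 45 takes an unadjusted two-sample t-test above 64%, and the omnibus ANOVA has 37% to 48% at N = 45.

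These figures assume 0.71 is the between-group difference in SD units and a two-sided 5% level before the planned Bonferroni correction, which would lower power wherever it is applied. The 15 v 15 and 11 v 11 figures also assume equal allocation; the ceiling does not. Nothing is concluded about quadriceps strength, gait speed, walking endurance or the within-person stimulated v unstimulated walking comparison, because Appendix A gives no effect size for them.

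**What to change.** Change the text of Participation Selection and Randomization and of Appendix A:

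- Label the two-group column as per group. At effect size 0.71, 32 per group means 64 evaluable for one two-group comparison and 96 (3 × 32) for pairwise comparisons among three groups. Do not present 96 as an ANOVA total: under the two mean patterns above, N = 96 gives 71% or 83%. Strictly, 32 per group gives 79.8%, and 33 is needed to pass 80%.
- Remove the statement that 32 participants in total give 80% power.
- Replace it with the approximate power for WOMAC-Function by an unadjusted two-sample t-test before multiplicity correction (about 47% at 15 per group, about 35% with 32 completers). Alternatively, give the effect detectable with 80% power (d about 1.06 at 15 per group, 1.26 at 11 per group).
- State the equal-allocation assumption and the SD to which 0.71 refers.

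The cost is a less favourable stated power. The 45 participants, the design and the tests can stay as planned.

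### The 32 participants called sufficient for 80% power are the per-group WOMAC-Function figure; at 45 over three arms neither WOMAC-PF nor WOMAC-Pain has 80% between-arm power, and strength and walking have no calculation

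*Combined protocol and SAP*

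**What the plan says.** Under Participation Selection and Randomization the protocol states: "A sample size of 32 participants was calculated to be sufficient for a two-tailed significance level of 5% and a power of 80" per cent. It refers to Appendix A and raises the number to 45 for dropouts, without giving a dropout rate. The sentence names no outcome and does not say whether 32 is a total or a number per group.

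Overview of Study sets up three groups and four co-equal primary outcomes: "Primary outcome measures of the study are quadriceps strength, perceived functional capacity, self-reported pain, and walking performance". The Walking Performance section defines the last of these by gait speed (10mWT) and endurance (6MWT).

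Appendix A uses power 0.8 and "Significance Level (alpha) = 0.05". Its table has three rows, all from the WOMAC. Each gives an effect size, a paired sample size and a between-group sample size:

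- "WOMAC - Function bivariate 0.71 ²⁷ 18 32"
- "WOMAC - Pain bivariate 0.41 ²⁷ 49 94"
- "WOMAC - Function Standing/Walking bivariate 0.45 ²⁷ 41 78"

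The last column is headed "Required sample size when comparing group A to group B", with no statement of per group or total.

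The Data Analysis section plans paired tests within a condition, ANOVA or Kruskal-Wallis across conditions, and a Bonferroni correction whose number of tests is not given.

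**The concern.** The sufficiency statement carries no limit, but the appendix behind it supports the number for one primary outcome of four. For pain, the same table asks for more participants than will be enrolled, whichever column is used. For strength, gait speed and walking endurance it offers nothing. In addition, a figure for each of two groups seems to have become the total for three.

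Objective 1 compares stimulation with conventional exercise on strength, function and pain, and Aim 2 seeks statistically significant evidence. Anyone interpreting a non-significant arm comparison would set it against a stated power of 80% that the design does not have.

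**Working it through.** **Inputs.** From Appendix A: effect sizes (d) 0.71, 0.41 and 0.45, alpha 0.05, power 0.8. Two-sided testing, 32 and 45 come from Participation Selection and Randomization; three arms from Overview of Study. Assumption: equal allocation, since no ratio is stated. That gives 45/3 = 15 per arm as enrolled and 32/3 = 10.67 per arm if the dropout allowance is used up (45 − 32 = 13; 13/45 = 28.9%).

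**Step 1: reproduce Appendix A.** By the normal approximation, n per group = 2(1.960 + 0.842)²/d² = 2 × 7.849/d². The two t columns solve for 80% power with the noncentral t distribution.

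| Row | d | Normal, per group | Two-sample t, per group | Printed | Paired t | Printed |
|---|---|---|---|---|---|---|
| Function | 0.71 | 15.698/0.5041 = 31.1, so 32 | 32.1 | 32 | 17.6 | 18 |
| Pain | 0.41 | 15.698/0.1681 = 93.4, so 94 | 94.4 | 94 | 48.6 | 49 |
| Standing/Walking | 0.45 | 15.698/0.2025 = 77.5, so 78 | 78.5 | 78 | 40.7 | 41 |

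All six printed figures reproduce. The last column does so only as a number per group: for d = 0.71 the two-group total is 64 (normal) or 66 (t), and a one-sided test would give 25.2 per group.

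**Step 2: compare with the trial.**

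- Function needs 32 per group; the trial has at most 15.
- Pain between groups needs 94. Enrolment of 45 falls short whether 94 is read as per group or as a total.
- Pain paired needs 49. Even pooling all 45, which is not a planned test, falls short.

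**Step 3: two-arm power at the actual size.** Noncentral t, 2n − 2 degrees of freedom, noncentrality d√(n/2), two-sided 5%, unadjusted.

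| n per arm | WOMAC-PF, d = 0.71 | WOMAC-Pain, d = 0.41 |
|---|---|---|
| 15 | noncentrality 1.944, power 46.7% | 1.123, 19.2% |
| 10.67 | 1.640, 34.4% | 0.947, 14.7% |
| 32 (for reference) | 2.840, 79.8% | 1.640, 36.5% |

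The planned three-arm ANOVA does no better. If the largest difference between arms is d, total 45 gives 37% to 48% for function and 15% to 18% for pain, depending on where the third mean lies.

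**Step 4: paired power within one arm of 15.** Noncentrality d√15: function 2.750, power 72.5%; pain 1.588, power 31.6%.

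**Step 5: outcomes without an effect size.** The documents give no standard deviations for strength, 10mWT or 6MWT, so only standardised detectable differences at 80% power can be stated.

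- Between two arms: 1.06 SD at 15 per arm, 1.28 SD at 10.67 per arm.
- Within person (stimulated versus unstimulated walking, Objective 2): 0.78 SD of the differences at n = 15, or 0.53 at n = 30 if both stimulated arms are pooled.

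**Step 6: multiplicity.** Appendix A uses unadjusted 0.05. If Bonferroni were split over the four primary outcomes (assumption, 0.05/4 = 0.0125), the t solution would rise to 46 per group for function and 135 for pain. Wherever the correction is applied, the powers above fall.

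**The case against.** The best defence is that nothing is miscalculated. Appendix A reproduces in full, the protocol points to it, and it prints 49 and 94 for pain openly. Sizing a trial on one outcome is legitimate. All of that stands. A reader might infer that the plan claims 80% power for every primary outcome, or that the appendix contains an arithmetic error; the documents support neither. The defect is an unqualified sentence that names neither the outcome nor the unit of its number, and that uses a per-group figure as the total for three arms.

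A sponsor may point to the Standing/Walking row as the calculation for walking. It is a WOMAC questionnaire score, not gait speed or endurance, and its 41 paired or 78 between groups also exceeds 32. A figure in Appendix A is not visible to us, but the table's pain row stands whatever that figure shows.

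It is also fair that between-arm detectable differences do not describe all the walking analyses. Objective 2 compares unassisted with assisted walking, and participants assigned stimulation walk under both conditions, so 1.06 to 1.28 SD would misstate that comparison. The paired figures apply there.

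Finally, no passage says that a non-significant result will be read as no effect. That is a risk of interpretation, not something planned.

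**Conclusion.** The point holds. The figure of 32 is the per-group requirement for WOMAC-Function at d = 0.71, and 45 participants over three arms do not give 80% between-arm power for WOMAC-PF or WOMAC-Pain at the Appendix A effect sizes. Between-arm power is roughly one in two to one in three for function, and one in five to one in seven for pain. The within-arm paired test at 15 also falls short for both outcomes. For strength and the walking tests no power can be stated from the documents.

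A tempting inference is that the shortfall is confined to the other primary outcomes and that WOMAC-PF keeps its 80%. The table does not support that: 80% belongs to 32 in each arm, more than twice the 15 enrolled per arm.

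These results rest on equal allocation, unadjusted two-sided 5%, approximate normality and the plan's own effect sizes. Reading the last column as per group is an inference from the arithmetic, but the shortfall for pain does not depend on it.

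**What to change.** 1. In Participation Selection and Randomization, say that 32 is the per-group figure for WOMAC-PF and that the trial does not have 80% between-arm power for WOMAC-PF or WOMAC-Pain at their Appendix A effect sizes. Label the last column of Appendix A as per group.
2. Add to Appendix A, with equal allocation and unadjusted two-sided 5% stated as assumptions:
   - two-arm power at 15 per arm and with 32 completers: WOMAC-PF 47% and 34%, WOMAC-Pain 19% and 15%;
   - paired power within one arm of 15: WOMAC-PF 72.5%, WOMAC-Pain 32%;
   - for strength and between-arm walking comparisons, a detectable difference of 1.06 SD (15 per arm) to 1.28 SD (32 completers);
   - for stimulated versus unstimulated walking within person, 0.78 SD of the differences at n = 15, or 0.53 at n = 30 if both stimulated arms are pooled.
3. Note that the planned Bonferroni correction lowers all these powers.
4. State that all four primary outcomes, WOMAC-PF included, will be reported with confidence intervals, and that non-significance on any of them will not be read as absence of effect.

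The cost is wording and a short table. Recruitment and conduct do not change; the price is a less favourable stated power.

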This protocol describes a study intended to evaluate the Cionic Neural Sleeve for subjects diagnosed with KOA. CIONIC will use this study as an opportunity to validate FES for disuse atrophy in KOA. CIONIC will use lab visits (Table 1) to record participants' strength, kinematic gait metrics, walking performance, self-reported functional capacity and pain.

The Cionic Neural Sleeve has been evaluated for safe use in a simulated at-home environment under prior studies (CIONIC-02-001 and CIONIC-03-001).

There are two specific aims with this study:

Aim 1 – Validate FES for disuse atrophy in KOA

The study intends to obtain evidence to support the use of the FES for disuse atrophy in the KOA community. Standard clinical assessments will be collected at meaningful endpoints in the study to allow CIONIC to measure subjects' performance over time.

Aim 2 - Provide statistically significant evidence

The study design is a randomized controlled trial, where CIONIC will collect spatial and kinematic metrics to track participants' mobility and gait patterns. Some examples of these metrics may include: gait speed, total steps, step variability, and foot-floor angle at heel strike.

Table 1: Schedule of events

Initial visit	
 • Verify consent • Gather demographic information and anthropometric measurements • Measure strength, walking performance, thigh muscle volume, functional ability of the lower limb • Distribute questionnaires on perceived functional capacity, pain, and quality of life • Prescribe exercise and walking program • Random assignment of groups • Distribute the Cionic Neural Sleeve and provide Instructions for Use
6 week study midpoint	
 • Measure strength, walking performance, thigh muscle volume, functional ability of the lower limb • Distribute questionnaires on perceived functional capacity, pain, and quality of life
End of study	
 • Measure strength, walking performance, thigh muscle volume, functional ability of the lower limb • Distribute questionnaires on perceived functional capacity, pain, and quality of life • Collect equipment

Participation Selection and Randomization

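### No test stimulation is described before randomisation, so the inadequate-response exclusion, if applied once assigned stimulation starts, can exclude people only from the two stimulated arms and could bias comparisons with control

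*Combined protocol and SAP*

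**What the plan says.** **The criterion.** Exclusion Criteria lists "Inadequate response to stimulation, as defined as inability to achieve muscle contraction or tolerate stimulation". The inclusion criteria add a companion requirement, that the device can be tolerated for up to an hour at a lab session. People who used FES in the past year are excluded.

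**Screening.** Under Overview of Study, "Participants will be screened for eligibility through a questionnaire", and eligible people are invited to the site after consent. The video call covers understanding, willingness, study details and capacity (Participation Selection and Randomization; Participant Identification, Recruitment & Informed Consent; Participant Capacity and Comprehension).

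**Allocation.** Table 1 puts "Random assignment of groups" at the initial visit, listed after the baseline measures and before the sleeve is handed out. The assigned intervention starts at that same visit.

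**Controls.** "The control group will not receive stimulation for the exercise and walking program" (Overview of Study). Walking Performance has them do the walking tests without stimulation as well. Under Lab Visits, only those assigned to stimulation learn to adjust it.

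**After entry.** Study Withdrawal lets investigators or the sponsor take people out for non-compliance and for broad administrative or medical reasons. Data Analysis/Statistical Analysis compares conditions by ANOVA or Kruskal-Wallis. It names no analysis population and no rule for missing data.

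**The concern.** An eligibility rule is harmless to a randomised comparison when it is applied to everyone before allocation. This one can be judged only by stimulating the person, and the first stimulation in the readable text is the assigned one. Followed as written, a person who cannot contract or cannot tolerate stimulation comes to light only in NMES+ or NMES+FES. An identical person in the control arm is never found and stays in.

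If those found are then removed and left out of the analysis, the stimulated arms become a selected group and the control arm does not. The hypothesised benefit is stimulated versus unstimulated, so the selection falls on the contrast of interest. A link between contraction response and quadriceps strength, one of the primary outcomes, is plausible, although the protocol does not document one.

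**Working it through.** **1. When the criterion can first be observed**

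| Step | What the text provides | Can it show response to stimulation? |
|---|---|---|
| Questionnaire | Self-report against the criteria; FES users in the past year excluded | No; few candidates could report a recent response |
| Video call | Understanding, willingness, capacity | No |
| Table 1, initial visit | Baseline measures, assignment, sleeve distribution | No test stimulation listed |
| Lab Visits, task order | Nine tasks | No test stimulation listed |
| Assigned intervention | Stimulation in NMES+ and NMES+FES only | Yes, in those two arms, after allocation |

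**2. Timing of assignment.** Table 1 lists assignment after the baseline measures. Lab Visits makes stimulation during the walking tests depend on group, and Walking Performance has stimulated subjects walk unstimulated first and stimulated second. If that applies at the initial visit, group is already known by the second 10-meter walk, the fifth of the nine tasks. The two accounts place allocation at different points, so the protocol fixes no clear pre-allocation window.

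**3. The planning effect used as a yardstick.** Appendix A, row "WOMAC - Function bivariate", gives effect size 0.71 and 32 under "Required sample size when comparing group A to group B", at two-sided 5% and 80% power. Check: 2 × (1.960 + 0.842)² / 0.71² = 31.1, rounded up to 32 per group. The figure reproduces. (The main text presents 32 as the total for three arms; that is a separate matter.) The 0.71 refers to WOMAC function, so it gives only a sense of scale for other outcomes.

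**4. Size of the bias, by correlation.** The documents give neither the failure rate nor its relation to outcome; both are assumptions. Let the lowest share p on a normal response trait be removed from a stimulated arm and none from control, and let r be the correlation of that trait with outcome. With no true effect, the apparent difference is r × φ(z_p) / (1 − p) SD.

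- p = 10%: φ(−1.282) / 0.9 = 0.1755 / 0.9 = 0.195
- p = 20%: φ(−0.842) / 0.8 = 0.2800 / 0.8 = 0.350

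| p | r = 0 | r = 0.3 | r = 0.5 | r = 0.7 |
|---|---|---|---|---|
| 10% | 0 | 0.06 | 0.10 | 0.14 |
| 20% | 0 | 0.11 | 0.18 | 0.25 |

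The non-zero cells are 8% to 35% of 0.71.

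**5. Size of the bias, without a distributional form.** If a fraction f is removed from a stimulated arm and those removed differ from those kept by g SD, the bias is f × g. Type I error for one two-sided comparison with control comes from the noncentral t, with noncentrality f × g / √(1/15 + 1/[15(1 − f)]). This assumes 45 participants allocated 1:1:1 (the ratio is not stated), no other dropout and no multiplicity adjustment.

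| f | g | Bias (SD) | Type I error |
|---|---|---|---|
| any | 0 | 0 | 0.050 |
| 10% | 0.5 | 0.05 | 0.052 |
| 20% | 0.5 | 0.10 | 0.057 |
| 20% | 1 | 0.20 | 0.079 |
| 30% | 1 | 0.30 | 0.110 |

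If all randomised participants are followed and analysed as assigned, this selection bias is 0 in every row.

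**6. How likely the situation is to arise.** With 30 stimulated participants, the chance of at least one failure is 1 − (1 − f)³⁰: 45% at f = 2%, 79% at 5% and 96% at 10%.

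**The case against.** Two stronger readings are tempting, and the documents support neither.

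*That the criterion can only remove people after randomisation.* Allocation happens at an in-person visit, with the device on site and a physical therapist present (Risk Mitigation Strategies, item 5). A prior check of everyone is feasible and nothing forbids it. Table 1 is a summary that also leaves out planned items such as EMG collection, which Table 2 lists. Figures 2 and 3, the study flow and recruitment plan, were not available for this review and may show such a step. All of this stands. It means the text has to state the step; it does not show that the step is planned.

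*That every comparison with control would be biased.* Bias needs four things: the criterion is applied after allocation, those who fail are removed, they are left out of the analysis, and failure is related to the outcome. No passage says that such people are dropped, and none says that they are kept. The removal clause applies to any arm. No link to pain, gait speed or quality of life is argued anywhere, and intolerance, the other limb of the definition, has no stated relation to strength. For change from baseline even the direction is open, since weaker people might gain more or less.

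The assumed failure rates may also be high. Lower motor neuron disease, absent sensation and neurological disease are already excluded in all arms, and participants set the intensity to their own comfort. At the milder inputs the type I error barely moves (0.052 to 0.057). That is a fair limit on the size. It does not supply the missing step or the missing analysis set.

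**Conclusion.** The concern holds as a conditional risk. The criterion needs a test stimulation, none is described before allocation, and controls are never stimulated. If it is applied once assigned stimulation starts, it can exclude only from NMES+ and NMES+FES. The general removal clause permits that, and the statistical section does not guard against it. Comparisons with control could then be biased, by an amount and in a direction that are unknown and may differ by outcome.

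The range of about 0.06 to 0.25 SD rests wholly on assumed removal of 10% to 20% and assumed correlations of 0.3 to 0.7, and zero belongs in the range. This is more than a missing detail, because closing the gap changes the order of trial steps. It should be corrected, since the remedy is cheap; it is not a demonstrated failure of the design.

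**What to change.** 1. Add to Table 1, at the initial visit and before the allocation is opened, a brief stimulation response and tolerance check for every candidate. Apply this exclusion and the device-tolerance inclusion criterion at that point only.
2. Reconcile Table 1, which lists assignment after the baseline measures, with Lab Visits and Walking Performance, which enable stimulation by group during the walking tests.
3. State in Data Analysis/Statistical Analysis that all randomised participants, including any who later prove intolerant, are followed for outcomes and analysed in their assigned arm. This concerns follow-up and analysis only; whether stimulation continues for a given person remains a clinical decision.

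**Cost.** A few minutes per candidate with a device already on site, and a protocol amendment. Controls receive one brief stimulation exposure, and some candidates will fail screening at the visit. If the check is already done in practice, the cost is writing it down.
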